#### 10.2.4. Statistical expression

The results of repeated measurements were presented in tabular form with statistical graphs in order to easy read.

In general statistical tests, bilateral tests were used. If P was less than or equal to 0.05, it would be considered that the discriminant of the test was statistical significance.

#### 10.2.5. Statistical software

The database was established by MS Access

SPSS/SAS software was used for analysis.

#### 10.2.6. Contents of statistical analysis

The statistical analysis plan was written by the statistician, finalized before the database lock, and consisted of a variety of tables. The main contents of the analysis included:

Case distribution: different data sets in each group, case distribution in each center, comparison of total abscission rate, and detailed list of termination causes.

Comparability analysis: compared demographic data with other base-value indicators to measure the comparability of the two groups.

Effectiveness analysis:  $X^2$  test and t test were used for main indicators and global indicators. Since this study was a multi-center clinical trial, central effect on the efficacy indicators should be considered in the analysis.

Analysis of the factors affecting the efficacy: such as age, sex, disease type, disease condition and so on, there were significant differences between the two groups before the use of vaccine, or if there were significant related factors that affected the vaccine effect, these factors should be used as co-factors when comparing the vaccine effect between the two groups for variables,

---

covariance analysis or Logistic regression analysis was required. The combination of medication and so on needed a detailed list.

Safety analysis: firstly, according to the requirements of side effect correlation, the side effect and adverse reactions of the two groups were listed and described (including the number of cases of various side effects, the number of cases and the conversion rate of "normal to abnormal" or "abnormal intensification" of laboratory test indicators before and after the test), and the reasons and explanations were listed.

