#### **7.4. Follow-up examination**

The first examination was performed on the day of study start (D0). Follow-up was conducted every 7 days (i.e. D7, D14, D21, and D28) for all clinical examinations, all indicators of the trial, and routine laboratory examinations.

Side effect should be recorded during routine daily clinical examinations. If any side effect was found, follow up immediately and informed the researcher.

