#### 10.2.3. Analytical method

The experimental group was compared with the control group by superiority comparison.

Measurement data:  $X^2$  test, t-test, paired t-test, rank sum test, paired rank sum test and non-parameter test were used respectively statistical analysis to make statistical comparison and other methods.

Descriptive statistical analysis of side effect was performed.

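### Section 10.2.6 lets significance tests on the trial's own data choose the efficacy covariates from an open list, and does not rank the adjusted analysis against the unadjusted tests

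*Combined protocol and SAP*

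**What the plan says.** Section 10.2.3 sets up a two-group test: "The experimental group was compared with the control group by superiority comparison". For the main indicators, section 10.2.6 names the chi-square test, and its sentence continues "test and t test were used for main indicators and global indicators". The same section adds that, because the trial is multi-centre, the "central effect on the efficacy indicators should be considered in the analysis". No significance condition is attached to centre.

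The next paragraph of 10.2.6 deals with factors affecting efficacy, "such as age, sex, disease type, disease condition and so on". It has two triggers joined by OR. The first is that "there were significant differences between the two groups before the use of vaccine". The second reads "or if there were significant related factors that affected the vaccine effect". If either applies, "these factors should be used as co-factors when comparing the vaccine effect between the two groups", through covariance analysis or logistic regression.

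Section 10.2.4 sets a two-sided 0.05 level. Section 10.2.6 has the SAP finalised before database lock. Section 7.1 gives the main efficacy indicator only as immunogenicity, with no assay, variable or day. Section 7.4 schedules an examination covering all trial indicators from D0 onward.

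**The concern.** Both triggers are significance tests on the trial's own data, and the second needs the outcome. Finalising the SAP before lock therefore fixes the procedure but not the model. Three features leave room for choice:

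- **No fixed set.** The candidate list is open-ended. Two of its four examples describe disease, although the population is healthy people (Summary 5, section 4.1). The baseline value of the immunogenicity measure, the natural covariate for this endpoint, is not named.
- **Uninformative first trigger.** A baseline P value does not show whether a factor predicts the outcome.
- **No ranking.** The chi-square and t tests and the adjusted analysis all stand. Nothing says which result decides superiority.

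At stake are some power, a clear definition of the primary result, and control of the type I error if the more favourable analysis can be reported.

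**Working it through.** **Inputs.** From the plan: two-sided 0.05 (10.2.4), superiority comparison (10.2.3), two triggers joined by OR (10.2.6). The plan has no power figure to reproduce. Assumed: normal outcome with SD 1, 1:1 allocation, 15 or 30 per arm (10 and 50 in some runs), covariate–outcome correlation ρ of 0 to 0.7, and trigger tests also at 0.05.

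**1. Benchmark.** Fixed ANCOVA multiplies the variance of the group difference by 1 − ρ². Approximate power is Φ(δ√(n/2)/√(1 − ρ²) − 1.96). With n = 30 and δ = 0.6, δ√(n/2) = 0.6 × √15 = 2.324. For ρ = 0.3 / 0.5 / 0.7 this gives Φ(0.476) / Φ(0.723) / Φ(1.294) = 68% / 77% / 90%. Simulation, which uses the t distribution, gives 66% / 74% / 89%.

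**2. How often the second trigger admits a covariate.** By Fisher's z, the chance is about Φ(atanh(ρ)√(N − 3) − 1.96).
- One covariate, N = 60: ρ = 0.3 gives Φ(2.337 − 1.96) = 65%; ρ = 0.5 gives Φ(4.147 − 1.96) = 99%; ρ = 0.7 gives over 99.9%.
- Four independent covariates sharing a joint ρ of 0.7 equally have 0.7/√4 = 0.35 each. N = 30 gives Φ(1.899 − 1.96) = 48% each; N = 60 gives Φ(2.759 − 1.96) = 79% each.

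A single strong predictor is nearly always admitted. Several moderate ones are often missed.

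**3. Power, rule as written against fixed ANCOVA (simulated).**

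| Setting | Rule | Fixed |
|---|---|---|
| 1 covariate, 30 per arm, 0.6 SD, ρ 0.3 / 0.5 / 0.7 | 66 / 74 / 89% | 66 / 74 / 89% |
| 4 covariates, 15 per arm, ρ 0.7 | 77% | 83% |
| 4 covariates, 30 per arm, ρ 0.7 | 83% | 86% |

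The plan does not say whether association is tested with group in the model, and this matters. A second set of runs put unadjusted power at 80% by normal approximation. With four covariates and ρ = 0.7, these gave 0.850 against 0.937 at 15 per arm (8.7 points), 0.926 against 0.957 at 30 (3.1 points) and 0.960 against 0.966 at 50 (0.6 points). The larger loss at 15 per arm arises when association is tested without group in the model. With ρ = 0 the rule has 0 to 5 points more power than fixed adjustment.

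**4. Type I error of the rule itself.** In the first row of the table, null rejection was 4.9–5.5%. Across the wider one- and four-covariate runs it was 0.047–0.053, against 0.047–0.054 for fixed ANCOVA. With ten candidates, none prognostic, and association tested given group, it was 0.072 (15 per arm) and 0.064 (30 per arm). The unadjusted test gave 0.058 and 0.053 in the same runs. The Monte Carlo standard error is √(0.05 × 0.95/6000) = 0.003.

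**5. Type I error if the better of the unadjusted and rule-based results is used.** It cannot exceed roughly 2 × 0.05 = 0.10.
- One covariate, ρ = 0.5: 0.071 (15 per arm) and 0.078 (30 per arm).
- One covariate, ρ = 0.7: up to 0.085.
- Four candidates, one prognostic at ρ = 0.5: 0.079 and 0.074.
- One covariate, ρ = 0: 0.053 and 0.044, so the excess needs a prognostic covariate or many candidates.

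**6. False baseline triggers.** With four independent covariates in a randomised comparison, the chance of at least one is 1 − 0.95⁴ = 18.5%.

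**The case against.** The strongest reply is that the rule does little harm as written. The second trigger admits exactly the factors that matter, so in a one-covariate setting power equals that of fixed ANCOVA and the error rate is nominal. With useless covariates the rule does slightly better. This stands, and it limits the point.

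A reader might infer that a strong predictor is dropped whenever it happens to be balanced, with a loss of up to 24 points (64% against 88% at ρ = 0.7, 30 per arm). That describes a rule with the baseline trigger alone. Section 10.2.6 joins the outcome trigger by OR, and step 2 shows that it almost always fires for such a predictor. Nor does the rule by itself break the 5% level. The baseline trigger alone is conservative (0.037–0.043 at ρ 0.5 to 0.7), and both triggers together are close to nominal with few candidates.

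Centre also falls outside the criticism, since the plan considers it without a trigger. The paragraph could be read as supplementary to the chi-square and t tests, but the plan does not say so, and that silence is the ranking problem.

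Finally, the Summary (item 4) and section 4.1 describe a single arm, and section 4.2 lists only a test group. On that design there is nothing to adjust. This makes the point conditional. It does not remove it, because sections 6.3, 10.2.1, 10.2.3 and 10.2.6 still plan a control group, randomisation and a two-group comparison.

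**Conclusion.** The point holds as a modest pre-specification defect, and only if the design is settled as two groups. The covariates are chosen by significance from an open list, one trigger uses the outcome, and the adjusted and unadjusted results are unranked.

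On the assumed 15 to 30 per arm, the power cost is close to nil with one prognostic covariate and about 1 to 6 points with four. It approaches 9 points at 15 per arm if association is tested ignoring group. The error rate stays near 5% if the rule is followed mechanically with few candidates. It reaches about 7–9% if the better of the two results is used with a covariate of ρ 0.5 to 0.7. The plan leaves that choice open; it does not state an intention to make it.

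Sample sizes, effects and correlations are all assumptions, and the logistic model was not simulated.

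**What to change.** First reconcile the one-arm and two-group passages.

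If a two-group comparison is kept, replace the trigger rule in 10.2.6 with one primary model: ANCOVA, or logistic regression for a binary outcome. Use a short fixed covariate set whatever any significance test shows: the baseline value of the primary immunogenicity measure if it is taken at D0, age, sex, and centre if there is more than one. Section 7.1 must name the measure and the day before this can be written. Label the unadjusted tests and any other adjusted models as sensitivity analyses.

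If the one-arm design is kept, delete the paragraph.

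The cost is wording, plus confirmation that the immunogenicity sample is taken at D0. Statistically it uses a few degrees of freedom and gives slightly lower power if the covariates prove non-prognostic and the groups are small.

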### 4. Overall design of test

This study was conducted in a single arm design.

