## 4. Overall design and arrangement of the test

### 4.1. Test design

This study adopted a one-arm experimental design. The whole study mainly collected qualified normal healthy people without disease from the hospital, and excluded people with basic diseases such as hypertension, diabetes, hyperlipidemia and so on. Once confirmed, they were assigned to administer 1 dose of Bacillus subtilis spore. Follow-up observation and efficacy examination were performed on days 7, 14, 21 and 28.

If subjects had significant laboratory abnormalities or side effect at the end of the study, they should be followed up to normal.

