## 7.3. Security indicators

General data: physical examination

Laboratory examination: Routine blood examination (including erythrocyte count, leukocyte count, hemoglobin, platelet count, proportion of monocytes, lymphocytes and neutrophils), urine routine (erythrocyte, leukocyte, urine protein), liver and kidney function (including ALT, AST, TBIL, BUN, Cr).

Symptoms accompanying any discomfort were recorded by the investigator

a) No: No symptoms

- b) Mild: Weak symptoms sometimes appeared
- c) Moderate: persistent but not noticeable after distraction
- d) Severe: Persisting no matter when

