## 11. Quality control and assurance

### 11.1. Quality control

During the study, clinical inspectors will be commissioned by the sponsor to visit each study center regularly to ensure that all the contents of the study plan were strictly followed and the study data were filled in correctly.

The whole clinical trial process strictly followed the provisions of the national GCP (Good Clinical Practice) and conformed to the ethical principles. Participants might strictly abide by the standard operating procedures of clinical trial study.

Participants in clinical trials should be relatively fixed, and participants might undergo uniform training and had uniform recording methods and judgment criteria.

The researcher should fill in the CRF truthfully, carefully and use pen or carbon pen.

All observations and findings in clinical trials should be verified to ensure the reliability of the data and to ensure that the conclusions of clinical trials were derived from the original data. There were corresponding data management measures in clinical trial and data processing stage.

Medical records and medical record forms were regarded as the original records and generally could not be changed. When making any corrections, the original record should not be altered. Additional statement could be used to explain the reason, and then signed and dated by the physician participating in the clinical trial.

The researchers should take active measures (notice further consultation, follow up) to control the shedding rate within 20%.

Subjects would record their vaccination status on a diary card.

Each center should submit its normal range and abnormal judgment criteria to the responsible unit of clinical trial and the clinical statistical unit to ensure the accuracy, reliability and abnormal judgment criteria of laboratory examination.

All laboratory data should be recorded in the original medical record and the results of the tests should be glued to the original medical record. Laboratory data within the normal range should also be recorded in the CRF, and data that were significantly higher or outside the clinically acceptable range should be verified by the physician participating in the clinical trial to make the necessary statements.

Administration of vaccines:

Preservation conditions of experimental vaccine: under 23° C, sealed in a dark place.

---

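### The laboratory shift summary names only worsening, does not define the post-dose value and uses centre-submitted criteria; if the trial has one arm, its rate has no background to be read against

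*Combined protocol and SAP*

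**What the plan says.** The safety paragraph of section 10.2.6 lists and describes side effects. Within that list it gives, for laboratory tests, a count of cases and "the conversion rate of 'normal to abnormal' or 'abnormal intensification' of laboratory test indicators before and after the test". It names no shift from abnormal back to normal. It states no post-dose time point, grading scale or expected background rate.

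Section 7.3 defines the panel, beginning "Laboratory examination: Routine blood examination (including erythrocyte count, leukocyte count, hemoglobin, platelet count". It has 7 blood-count, 3 urine and 5 liver and kidney indicators, 15 in all. Section 7.4 sets a D0 examination and then repeats the routine laboratory tests: "Follow-up was conducted every 7 days (i.e. D7, D14, D21, and D28").

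On what counts as abnormal, section 11.1 says: "Each center should submit its normal range and abnormal judgment criteria to the responsible unit of clinical trial". The same section also asks for uniform training and uniform judgement criteria among those running the trial.

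On the number of arms, the sections disagree. Section 4.1 says "This study adopted a one-arm experimental design" and the Summary, section 4, says "This study was conducted in a single arm design". The dosing table in 4.2 has a test group only. Yet section 6.3 describes a control group, 7.2.3 records deaths for each group, and 10.2.3 plans a superiority comparison with a control. The sentence in 10.2.6 that contains the laboratory shifts itself says "the side effect and adverse reactions of the two groups were listed and described".

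**The concern.** Healthy people cross reference limits in both directions without any treatment. A summary that names only the crossings into abnormality shows half of that movement. To judge whether a conversion rate is more than drift, the reader needs either a concurrent control or the count of reverse shifts. Section 10.2.6 does not name the reverse shifts, and the documents do not settle whether a control exists.

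Two further gaps make the rate hard to interpret. With D7, D14, D21 and D28 all available, the after value could be the last panel, the worst panel or each panel in turn, and the answers differ widely. With criteria submitted by each centre and no common grading, the same result could count as a conversion at one centre and not at another.

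Safety is a stated objective (Summary, section 2; section 3). At stake is whether the reported rate can support a statement about laboratory safety in either direction.

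**Working it through.** The documents give no sample size, laboratory threshold or expected abnormality rate, so there is no planned figure to reproduce. What follows illustrates an inert product.

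**Inputs from the documents.** Indicators: 7 + 3 + 5 = 15 (7.3). Panels: one at D0 and four post-dose (7.4).

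**Assumptions, not in the documents.** Ten indicators have two-sided 95% limits (5% of values outside) and five have an upper limit only (2.5% outside). Values are Gaussian with a stable mean. Within-person correlation r runs from 0.3 to 0.9. Indicators are independent of each other.

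**Formulas.** Write a value as √r·u + √(1−r)·e, where u is the person's level and e is visit noise. Let p(u) be the chance that a value is abnormal given u. For a two-sided indicator, p(u) = Φ((−1.96 − √r·u)/√(1−r)) + 1 − Φ((1.96 − √r·u)/√(1−r)). For an upper limit only, p(u) is the last part, 1 − Φ(...). Averaging over u:

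- Normal at D0, abnormal at D28: E[(1−p)p]
- Normal at D0, abnormal at any of four visits: E[(1−p){1 − (1−p)^4}]
- At least one of 15 indicators: 1 − (1−a)^10 × (1−b)^5, where a and b are the two-sided and one-sided values

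**Example, r = 0.5.** At D28, a = 0.0407 and b = 0.0204. Among baseline-normal subjects the two-sided rate is 0.0407/0.95 = 4.3%. At least one of 15: 1 − 0.9593^10 × 0.9796^5 = 40%. Over any of four visits, a = 0.1328 and b = 0.0665, giving 1 − 0.8672^10 × 0.9335^5 = 83%.

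| r | One two-sided indicator at D28, baseline-normal | Any of 15 at D28 | Any of 15 at any of four visits |
|---|---|---|---|
| 0.3 | 4.8% | 44% | 88% |
| 0.5 | 4.3% | 40% | 83% |
| 0.7 | 3.5% | 35% | 72% |
| 0.8 | 3.0% | 30% | 63% |
| 0.9 | 2.1% | 23% | 48% |

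For a one-sided indicator the D28 rate runs from 2.3% down to 1.0%.

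**Sensitivity.** With narrower tails (2% two-sided, 1% one-sided), the last two columns become 21% down to 11% and 60% down to 26%. In a separate run with all 15 indicators at 5%, the any-visit share is 88%, 79% and 55% for r = 0.5, 0.7 and 0.9. Correlating the indicators at 0.3 lowers it to 83%, 73% and 50%.

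**Reverse shifts.** With no effect, D0 and D28 have the same chance q of abnormality. Then P(normal, abnormal) = q − P(both abnormal) = P(abnormal, normal). The two directions are equal whatever r is. Simulation with q = 5% agrees: 4.1% against 4.1% at r = 0.5, and 2.0% against 2.0% at r = 0.9. The reverse count is therefore a background estimate that the trial already collects.

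**The case against.** The strongest objection is that the sentence in 10.2.6 reports two groups. If a control is run, the background rate is observed directly and the lack of a benchmark disappears. That stands, and it is why the conclusion is conditional on the number of arms. A control would not settle which panel is the after value or which criteria define abnormal.

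Four stronger readings are tempting, and the documents do not support them.

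- *An inert capsule would necessarily show a high conversion rate.* The 48% to 88% pools 15 indicators over four visits. Section 10.2.6 does not say that indicators or visits are pooled. Read as each indicator at D0 against D28, the figure is a few per cent.
- *These shifts are the only laboratory summary.* They sit in an illustrative list. Sections 10.2.2 to 10.2.4 plan general summary statistics, paired tests, and tables and graphs of repeated measurements. Those provisions are generic, and none supplies a background rate for conversions.
- *Shifts will be called vaccine-induced.* Nothing says so. Section 10.2.3 makes side-effect analysis descriptive, 8.3 grades causality in five levels, 10.2.6 lists reasons, and 11.1 has a physician verify clinically out-of-range values.
- *Centre-specific criteria inflate the rate.* They add inconsistency but have no inherent direction, and local ranges properly allow for differences between laboratories. Section 11.1's request for uniform judgement criteria favours common grading, but it does not say how that fits with centre-submitted criteria.

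**Conclusion.** The point holds in a limited form. The named laboratory shift summary runs in one direction, has no defined post-dose value and rests on centre-submitted criteria that sit awkwardly with the same section's call for uniformity. If the one-arm statements stand, its rate cannot be separated from ordinary drift. If the control exists, it can, provided the shifts are reported by group. The sections on the number of arms must be reconciled first.

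Under the assumptions shown, the choice of reading alone moves the no-effect figure from about 2% to 5% (one two-sided indicator, D28) to 23% to 44% (any of 15, D28) and 48% to 88% (any of 15, any visit). The limits, the correlations, the split into ten and five, and the independence of indicators are all assumed. Positive correlation between indicators lowers the pooled figures somewhat. The equality of the two directions needs only that the chance of abnormality is the same at both visits and that subjects are not selected on their D0 values.

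**What to change.** First reconcile the one-arm statements (Summary section 4; 4.1) with those describing a control or two groups (6.3, 7.2.3, 10.2.3, 10.2.6).

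In 10.2.6, for each indicator and each of D7, D14, D21 and D28, report a D0-by-visit shift table. It should give both normal-to-abnormal and abnormal-to-normal counts and their paired difference, by group if a control exists. Keep worsening of an already abnormal value as its own cell. This also settles what the after value means.

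In 11.1, keep each laboratory's own normal range, but apply one common set of abnormality and grading criteria at all centres.

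Conversions seen at a single visit should stay in the main count. Making persistence the headline would move transient post-dose abnormalities out of the main safety figure. Confirming every D28 conversion would also need samples beyond the follow-up that 4.1 reserves for significant abnormalities. Persistence is at most a supplementary listing.

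The cost is slightly more tabulation and one grading table, with no new visits or samples. There is one limitation. To the extent that D0 abnormalities lead to exclusion, reverse shifts will be under-represented and the paired difference biased toward worsening. In the extreme, with every D0 abnormality excluded, no reverse shifts remain. The report should state how many enrolled subjects were abnormal at D0 for each indicator.
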